IMP	Investigational Medicinal Product
IMPD	Investigational Medicinal Product Dossier
MCA	Middle cerebral artery
METC	Medical research ethics committee (MREC); in Dutch: medisch ethische
	toetsing commissie (METC)
MSC	Mesenchymal stromal cell
NNRN	Dutch Neonatal Research Network; in Dutch: Nederlands Neonataal

	Research Netwerk
(S)AE	(Serious) Adverse Event
SPC	Summary of Product Characteristics (in Dutch: officiële productinfomatie
	IB1-tekst)
Sponsor	The sponsor is the party that commissions the organisation or performance
	of the research, for example a pharmaceutical
	company, academic hospital, scientific organisation or investigator. A party
	that provides funding for a study but does not commission it is not
	regarded as the sponsor, but referred to as a subsidising party.
SUSAR	Suspected Unexpected Serious Adverse Reaction
PAIS	Perinatal arterial ischemic stroke
UMCU	University Medical Centre Utrecht
Wbp	Personal Data Protection Act (in Dutch: Wet Bescherming Persoonsgevens)
WKZ	Wilhelmina Children's Hospital
WMO	Medical Research Involving Human Subjects Act (in Dutch: Wet Medisch-
	wetenschappelijk Onderzoek met Mensen

SUMMARY

Rationale: Perinatal arterial ischemic stroke (PAIS) is an important perinatal cause of longlasting neurodevelopmental problems. Recent studies report an incidence of PAIS of 1 per 2300 full-term infants born alive. Adverse consequences of PAIS include hemiplegia, cognitive dysfunction, epilepsy and speech problems. In 50-75% of infants, neonatal stroke leads to abnormal neuromotor and -developmental outcome or epilepsy. The estimated annual mortality rate of neonatal stroke is 3.49/100,000 annually. Current treatment options for PAIS mainly focus on controlling convulsions and associated infections. There is no treatment available that leads to reduction of neonatal brain damage in this severely affected group of infants. This leads to life-long consequences of PAIS and forms a large burden for patients and society. The overall aim of this project is to meet this need by developing a cell based treatment strategy.

Animal models of neonatal brain injury provide evidence for the feasibility and efficacy of intranasal mesenchymal stromal cell (MSC) application in the treatment of PAIS. Additionally, results from human trials with MSCs in the treatment of adult stroke or other pathologic conditions provide evidence that MSC treatment is safe. This project aims at making the first step towards clinical application of MSCs to treat PAIS. Successful completion of this project will provide the first evidence of the safety and feasibility of MSCs to treat brain damage in newborn infants.

Objective: This study will assess safety and feasibility of bone marrow-derived allogeneic MSCs, administered by the nasal route, in neonates who suffered from PAIS.

Study design: A phase I/II, open-label, single-arm, single-center intervention study in the NICU at the Wilhelmina children's Hospital / University Medical Centre in Utrecht of (near-)term newborns ≥36 weeks of gestation within the first week of onset of presenting clinical symptoms.

Study population: All (near-)term newborns ≥36 weeks of gestation with or without clinical symptoms of PAIS but with a magnetic resonance imaging (MRI) confirmed PAIS (in the MCA region) will be eligible for this study. Following written parental consent, 10 patients will be included in our study.

Intervention: One dose of 50x10⁶ MSCs via the nasal route as soon as possible after confirmation of the MCA-stroke, but within the first week of onset of presenting clinical symptoms. Within 30 minutes after cleaning the nose with saline, using standard procedures operative at the NICU, the MSC will be delivered.

Main study parameters/endpoints: Our primary objective is to determine if MSC treatment in neonates with PAIS is safe in the acute setting, including vital signs at time of treatment, blood sampling before and after MSC treatment and occurrence of any adverse events.

Secondly we will investigate subacute and long-term safety of MSC treatment at 3 months, in terms of SAEs (such as infections) and cerebral tumorigenicity on MRI. Follow-up assessment at 3 months is part of regular care for neonates with PAIS.

Nature and extent of the burden and risks associated with participation, benefit and group relatedness: The extra burden of the present study for the included infants is considered to be very limited to non-existent given the fact that besides the nasal treatment to apply the MSCs, treatment is not different compared to the standard acting treatment protocol for newborns with PAIS. Nasal application of MSCs has been considered as noninvasive. With respect to possible risks of the present MSC treatment, the most important potential risk factors such as inflammatory actions of MSC therapy with allogeneic human MSCs and an increased risk for malignancies, have been intensively investigated in our own preclinical studies and appear to be non-present at long-term follow up. Additionally, human trials on MSC treatment for adult stroke or other pathologic conditions do not provide evidence for these or other serious adverse events or risks. No single indication has been found in experimental research in the developing animal models that above mentioned complications occur in a higher incidence as compared to non-MSC treated animals, whereas possibility for a substantial better short- and long-term outcome seems very realistic on the basis of previous experimental research data. This study will assess safety bone marrow-derived allogeneic MSCs, administered by the nasal route, in human neonates with PAIS.

[figure not shown]
INTRODUCTION AND RATIONALE

Introduction

Perinatal arterial ischemic stroke (PAIS) or cerebral infarction is an important perinatal cause of long-lasting neurodevelopmental problems. Recent studies report an incidence of PAIS of 1 per 2300 full-term live births.(Kirton & DeVeber 2009) PAIS has been diagnosed mostly in the first week of life.

PAIS occurs most often in de middle cerebral artery (MCA) with a predilection for the left MCA.(Fernández-López et al. 2014; Benders et al. 2014; Kirton et al. 2011; van der Aa et al. 2014) The most important risk factors are associated with pathological changes that manifest during pregnancy and delivery. Important maternal risk factors include gestational diabetes, pregnancy-induced hypertension and pre-eclampsia, while perinatal factors associated with neonatal stroke are ventouse delivery, emergency Caesarean section, perinatal infections and hypoglycaemia.(Fernández-López et al. 2014; Kirton et al. 2011; Harteman et al. 2012; Martinez-Biarge et al. 2016) Placental pathology has also been linked to PAIS.(Elbers et al. 2011) Coagulation disorders are associated with neonatal stroke, such as genetic polymorphisms of prothrombotic factors (e.g. Factor V Leiden, prothrombin, lipoprotein (a), methylenetetra-hydrofolate reductase or acquired prothrombotic states (e.g. activated protein C). These factors are increasing the risk for PAIS when combined with other risk factors such as perinatal asphyxia, congenital heart diseases or neonatal infections.(Fernández-López et al. 2014)

The disease manifests itself most often with one-sided convulsions in the first week after birth, often accompanied with (asymmetric) hypotonia, lethargy and apnea.(Kirton et al. 2011; van der Aa et al. 2014) When stroke is suspected clinically and on cranial ultrasound, this is usually confirmed by magnetic resonance imaging (MRI). Neuromotor outcome becomes more evident over time and depends largely on the involved cerebral structures. Especially involvement of the internal capsule and the basal ganglia is associated with impaired motor outcome.(figure 1)

[figure not shown]

Figure 1: Representative MRI of a full-term infant with a main branch MCA infarct on the left. The first scan was performed during the first week. The diffusion weighted images (left) shows restricted diffusion of the cortex, subcortical white matter and basal ganglia. A second MRI at 3 months of age (right) shows a large cavity with lack of myelination of the posterior limb of the internal capsule. Adverse consequences of PAIS include unilateral spastic cerebral palsy (USCP) cognitive dysfunction, epilepsy and speech problems. In 50-75% of infants, neonatal stroke leads to abnormal neuromotor and -developmental outcome or epilepsy.(Fernández-López et al. 2014) Recurrent seizures after PAIS are also often reported, with larger areas of stroke being more likely to be associated with postneonatal epilepsy and lower cognitive outcome. (Wusthoff et al. 2011; van Buuren et al. 2013) The estimated annual mortality rate of neonatal stroke is 3.49/100,000.(Lynch & Nelson 2001)

In adult stroke, treatment focuses on thrombolytic therapy and is, after exclusion of hemorrhagic stroke, standard part of care given within a timeframe of 6-8 hours after the event. Newborns usually present with less specific symptoms, which results in a later diagnosis of PAIS compared to adult stroke. Since neonatal stroke is usually diagnosed later, early treatment options, such as hypothermia used in perinatal asphyxia, with a therapeutic window of six hours after birth, cannot be used in neonatal stroke. Current treatment options for PAIS mainly focus on supportive care, such as controlling hypoglycaemia, treatment of convulsions and associated infections. There is no specific treatment available that leads to reduction of neonatal brain damage in this severely affected group of infants. This leads to life-long consequences of PAIS and forms a large burden for patients and society. The overall aim of this project is to meet this need by assessing the safety and feasibility of a cell based treatment strategy for neonates with PAIS.

Rationale

Mesenchymal stromal cells (MSCs) can be isolated from embryonic and fetal tissues, such as placental tissue, fetal blood, umbilical cord blood and stroma (Wharton's Jelly). Furthermore, they can also be isolated from adult tissues like bone marrow. MSCs can differentiate into mesodermal tissue cells (e.g. bone, cartilage, fat), but in vitro experiments have demonstrated that MSCs are, during and after hypoxia-ischemia, also capable to stimulate the formation of neurons, astrocytes, oligodendrocytes and microglia.(Kohyama et al. 2001; Dezawa et al. 2004)

From neonatal rat models of brain injury, we have learned that hypoxic- ischemic (HI) brain injury induces changes in neurovascular environment that promote neurogenesis.(Kadam et al. 2008; Ong et al. 2005; Yang & Levison 2007; Donega, van Velthoven, Nijboer, Kavelaars, et al. 2013) However, after HI brain injury, there is no induction and maintenance of long-term neurogenesis. Therefore it is crucial to assist the brain in regeneration after injury and

also to reinforce development of the maturating brain. In animal HI-model studies, it has been demonstrated that transplantation of murine adult bone marrow-derived MSCs markedly improves neuroregeneration. Treatment with MSCs stimulated formation of new neurons and oligodendrocytes and reduced infarct size by >45%. Although intracranial MSC treatment stimulated formation of new brain cells and differentiation of these cells into new neurons and oligodendrocytes, these newly formed cells were not of transplant origin. These findings indicate that the neuroregenerative effect of MSCs after ischemic brain damage mainly relies on stimulation of endogenous repair mechanisms.(van Velthoven et al. 2010c) This is confirmed by data from our group that show that MSC treatment has profound effects on the expression of growth and differentiation factors in the brain. For example, MSC treatment at 10 days after HI induces upregulation of 35 genes encoding factors that are mainly involved in cell growth and proliferation. MSC treatment at 3 and 10 days after induction of HI brain damage induces expression of 28 additional factors and these are predominantly involved in cell differentiation and nervous system development.(van Velthoven et al. 2010c; van Velthoven et al. 2011) These results show that the first dose of MSC stimulates cerebral cell proliferation, whereas the second injection enhances differentiation and maturation of newly formed cells and integration in a functional network.(van Velthoven et al. 2010c)

Based on these findings, we hypothesized that MSC of donor origin will only transiently survive in the brain and that the neuroregenerative effects of MSC are mediated predominantly by inducing changes in the growth factor milieu of the brain. The corticospinal tract is the primary transmission route for voluntary movement of the forepaws. We showed that MSC treatment could also partially restore the damaged corticospinal motor tract which led to improved sensorimotor outcome.(van Velthoven et al. 2010c; van Velthoven et al. 2010a)

MSCs have many advantages over other types of stem cells or progenitors. First of all, they can easily be obtained from infants and adults.(Le Blanc & Mougiakakos 2012) Additionally, as described above, MSC treatment have a long therapeutic window, as they can be administered at least until 10 days after brain injury to improve behavioral outcome and lesion volume in neonatal HI mice. This is of great value, since the only available therapies for HI injury have to be given within a few hours. Besides, MSCs are hardly detectable in the brain after 3 days (Donega, van Velthoven, Nijboer, van Bel, et al. 2013), so the risk of Hostversus-Graft is very low. It is also very unlikely that MSCs will cause other adverse effects if they are no longer present in the brain after a short period of time. Our most recent study showed no malignancies in the brains or in other organs of mice treated with MSCs when

assessed at 14 months after start of MSC treatment at 10 days after neonatal HI.(Donega et al. 2015) Furthermore, MSCs have low immunogenicity because they do not express major histocompatibility complex (MHC) class-II antigens.(Rocha et al. 2000; Uccelli et al. 2008; Fleiss et al. 2014) This makes them excellent therapeutic candidates for allogeneic treatment.

Another advantage of MSCs, is that they have proven to be effective in brain injury when administered intranasally. This is beneficial since it has been reported that systemically administered human bone marrow-derived MSCs migrate into peripheral organs but were not able to induce neuroprotective effects in the brain after cerebral ischemia.(Steiner et al. 2012) After systemic administration MSCs will also migrate to peripheral organs, leading to loss of MSCs in these organs (trapping).(Li et al. 2015; Liu 2011; Jiang et al. 2011) This may result in reduced migration of MSCs into the brain and will consequently diminish their neuroregenerative effects on the brain.(Li et al. 2015; Liu 2011; Jiang et al. 2011; Steiner et al. 2012) In newborns, trapping of MSCs in other organs will be more important than in adults. MSCs are attracted by areas of injury in the organ systems, (Wang et al. 2014) PAIS is related to fetal distress and subsequent hypoxia-ischemia.(Harteman et al. 2012; Martinez-Biarge et al. 2016) Other risk factors for PAIS are maternal fever, hypoglycemia and earlyonset sepsis/meningitis. (Harteman et al. 2012) These risk factors, as well as hypoxiaischemia, may lead to diffuse damage to other organ systems. When MSCs are administered systemically, they may be attracted by systemic damage, leading to even more trapping of the MSCs in other injured organs. This makes it difficult to predict if and how many MSCs will migrate to the brain when given systemically. Studies from our group and others have shown that MSCs when given intranasally migrate within two hours after administration to the ischemic brain region. (Donega, Nijboer, van Tilborg, et al. 2014) Intranasal administration of MSCs reduces lesion volume loss and improves sensorimotor outcome.(van Velthoven et al. 2010b; Wei et al. 2015). Efficacy of intranasal versus intracranial MSC treatment on lesion size and motor behavior was similar in the neonatal HI mouse model.(van Velthoven et al. 2012) Studies of our group in the newborn baboon have shown that intranasally administered MSCs have the potential to migrate to the injured brain region of primates (unpublished observations), in accordance with earlier shown studies in mice and rats. Overall, the intranasal administration route provides an effective alternative allowing MSC treatment for brain injury without invasive methods and minimal burden for the patient.

Even though all evidence on efficacy and feasibility of MSCs in the treatment of neonatal brain injury is based on animal models, there is evidence that human MSCs have the same potential. Human MSCs were found to improve sensorimotor function and decrease gray and white matter volume loss in our mouse model of HI brain injury.(Donega, Nijboer, Braccioli, et al. 2014) These findings are comparable to those of murine MSCs and strongly support the therapeutic potential of hMSCs for neonatal brain injury. Additionally, this study confirms the efficacy of (human) MSCs when administered intranasally.

There are no clinical trials published on MSC treatment for neonatal stroke. However, there are some studies available describing the treatment of adult stroke with MSCs. These studies may support the evidence for the use of MSCs in neonatal stroke, but it is important to realize that results from adult trials can not be directly translated to neonatal care for several reasons. First of all, the newborn brain has much better plasticity capacity than the brain of older children and adults. This causes the newborn to recover more easily after (severe) brain injury than an adult.(Bower 1990; Schneider 1970) Secondly, effectiveness of MSC treatment reduces with increasing age, because endogenous neurogenesis capacity also reduces with age. This causes neonates to have more potential to regenerate their damaged neurons and/or networks compared to adults.(Titomanlio et al. 2011; Bondolfi et al. 2004; Kuhn et al. 1996; Leuner et al. 2007) Lastly, neonatal stroke (PAIS) is a different disease, with different pathology and symptomatology, than adult stroke.(Comi & Johnston 2009)

However, the results from adult trials can be used to support safety and feasibility of MSC treatment in neonatal stroke. Clinical trials with MSC treatment for adult patients with ischemic stroke have shown some evidence for the efficacy of MSCs in the treatment of ischemic stroke. These studies described patients who were treated with MSC at 7-133 days post-stroke.(Bang et al. 2005; Honmou et al. 2011) Although the evidence is sparse, there are some trials, mainly uncontrolled open-label studies, that have demonstrated clinical neurological improvement in patients with acute and chronic stroke after treatment with MSCs.(Bang et al. 2005; Lee et al. 2010) Most importantly, these trials have not demonstrated any serious adverse events, such as neurological deterioration, systemic infections nor tumor development, related to MSC transplantation. This is also concluded from a meta-analysis on over 1200 patients treated with MSCs for various pathological indications. Only transient fever within the first days seemed to be related to MSC transfusion.(Lalu et al. 2012)

There is only one clinical trial describing the use of MSCs in treatment of neonates.(Chang et al. 2014) Chang et al. assessed in a phase I dose-escalation trial the safety and feasibility of intratracheal administration of allogeneic umbilical cord-derived MSCs in preterm infants with high risk for bronchopulmonary dysplasia (BPD). Importantly, there were no serious adverse events or toxicity related to a higher dose of 2 x 10⁴7 cells/kg.(Chang et al. 2014) These

findings were more recently confirmed by another group treating 3 premature infants with approximately 2 x 10⁶/kg bone marrow-derived MSCs intravenously.(Henckel et al. 2015) The authors concluded that intravenous MSC treatment was feasible, well tolerated and no effects on pulmonary and cerebral blood flow could be detected.(Henckel et al. 2015) An ongoing study in Korea is treating preterm infants with intraventricular hemorrhage with allogeneic umbilical cord MSCs, and preliminairy results are promising and show no adverse effects.(Presented at Pediatric Academic Societies Meeting, Baltimore, Monday May 2, 2016 - 8:00 am, E-PAS2016:3090)

Overall, MSC treatment under several pathologic conditions, including stroke, in adults and children appeared to be safe.

In summary, based on the available evidence there seems to be a solid basis for clinical translation. Animal models of neonatal brain injury provide evidence for the feasibility, efficacy and safety of intranasal MSC application in the treatment of PAIS. Additionally, results from human trials with MSCs in the treatment of adult stroke or other pathologic conditions, including BPD in neonates, provide evidence that MSC treatment is safe. This project aims at making the first step towards clinical application of MSCs to treat PAIS. Successful completion of this project will provide the first evidence of safety of MSCs to treat brain damage in newborn infants.

1. OBJECTIVES

Our primary objective is to determine if MSC treatment, in neonates with PAIS, is safe in the acute setting, including vital signs at time of treatment, blood sampling before and after MSC treatment and occurrence of any adverse events or toxicity. Secondly we will investigate safety of MSC treatment at 3 months, in terms of SAEs and tumorigenicity on MRI.

Primary Objective

• To determine if MSC treatment in (near-)term infants with PAIS is safe in the acute setting.

Safety is defined primarily as the absence of treatment-related serious adverse events (SAEs) according to the Consolidated Standards of Reporting Trials (chapter 7.2), secondly as the absence of dose-limiting toxicity, defined as death within 24 hours after MSC transplantation or anaphylactic shock related to the MSC administration. At least, all patients will be regularly and intensively assessed, including vital signs, before and 24 hours after treatment, until discharge from our hospital. Also, blood sampling will be performed before and 24 hours after treatment with MSCs to determine infection and inflammation parameters. Acute safety will be determined until discharge.

Secondary Objectives

- To determine if MSC treatment in (near-)term infants with PAIS is safe in the subacute setting.
 - Subacute safety is defined primarily as the absence of treatment-related serious adverse events (SAEs) according to the Consolidated Standards of Reporting Trials (chapter 7.2) until the age of 3 months. Patients will then be asked to report on other SAEs, including infections.
- To determine if MSC treatment in (near-)term infants with PAIS is safe at 3 months in terms of cerebral tumorigenicity.
 - To assess safety of MSC treatment on the brain, infants will be scanned using MRI prior to MSC treatment and at 3 months of age. Long-term adverse effects on the brain in terms of tumorigenicity will be determined using this MRI, which is part of regular stroke follow-up program.

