AEs and SAEs occurring during the study will be recorded in the manner described under Section 7.2. All SAEs will be followed up until resolution or until the event is considered stable. SAEs resulting in a life threatening condition or death will be reported to the regulatory authorities and the EC in line with the local regulatory requirements. In addition the investigator will report any SAEs resulting in death and/or a life-threatening situation and any unexpected related SAEs to the regulatory authorities and the Ethics Committee (EC) in line with the local regulatory requirements. An independent data safety and monitoring board (DSMB) has, in addition to an internal safety review committee, been established to carry out further safety surveillance (see Paragraphs 7.2.3 and 7.4).

[figure not shown]
MRI measurements

For secondary parameters, subjects will be scanned on a 3 Tesla MR scanner as soon as possible after clinical suspicion of PAIS and again 3 months after the MSC treatment. Further details on MRI measurements can be found in chapter 6. All infants will return to the WKZ, UMCU for a MRI scan at 3 months of age.

Follow-up

After the intervention period, subjects will be followed until 3 months corrected age. At 3 months neurological assessment will be performed as part of the regular stroke follow-up program. This will also include filming spontaneous and endogenous movements (General Movements). Additionally, fidgety movements will be assessed. Neuromotor development will also be assessed using the HINE. After parental consent, results from these examinations will be used for this study. Subjects in this study will also be followed for at least 2 years of age at regular time points. This follow-up is part of regular care for neonates with PAIS, but these results are not part of this study protocol and are beyond the scope of this study.

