6. METHODS

6.1 Study parameters/endpoints

6.1.1 Main study parameter/endpoint

Safety is defined primarily as the absence of treatment-related serious adverse events (SAEs) according to the Consolidated Standards of Reporting Trials (chapter 7.2 and bron), secondly as the absence of dose-limiting toxicity, defined as death within 24 hours after MSC transplantation or anaphylactic shock related to the MSC administration, and thirdly as the absence of adverse events at 3 months of age in terms of cerebral damage and neurodevelopmental outcome (see secondary outcome).

For acute safety, all patients will be regularly and intensively assessed, including blood sampling and vital signs, before and 24 hours after treatment, until discharge from our hospital. Also, blood sampling will be performed before and 24 hours after treatment with MSCs to determine inflammation parameters. Acute safety will be determined until discharge.

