6.7 Premature termination of the study

The study may be terminated prematurely for safety or futility reasons if there are AEs or SAEs as defined by chapter 7.

We will use the following stopping rules:

- If the region of infarction, as defined on T2 weighted MR imaging and/or DWI, increases by >20% after treatment with MSCs in 3 different patients.
- If there appear to be any adverse effects that might be related to admission of MSCs in 3 different patients. These adverse effects include:
 - Systemic infections / meningitis
 - o Hemorrhagic transformation of the infarction
 - Gastrointestinal hemorrhage
 - o Thromboembolism
 - Formation of malignancies
- Unexpected and unaccountable deterioration of clinical situation, for example persistent seizures, after treatment with MSCs in 3 different patients. Usually, stroke-related seizures will disappear within three days following their onset and treated with anti-epileptic drugs.
- Mortality after treatment with MSCs in one patient will stop the study temporarily until an investigation has been performed.

Continuation of the study will only take place after the first three infants completed their second MRI scan at 3 months of age. This will safeguard that all stopping criteria will be monitored closely and the study may be terminated prematurely in time when stopping criteria are met.

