7. SAFETY REPORTING

7.1 Section 10 WMO event

In accordance to section 10, subsection 4, of the WMO, the sponsor will suspend the study if there is sufficient ground that continuation of the study will jeopardise subject health or safety. The sponsor will notify the accredited METC without undue delay of a temporary halt including the reason for such an action. The study will be suspended pending a further positive decision by the accredited METC. The investigator will take care that all subjects are kept informed.

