7.5 Data Safety Monitoring Board (DSMB)

A DSMB will be established to perform ongoing safety surveillance and to perform interim analyses on the safety data. This committee will be an independent committee. The DSMB is composed of 4 members from the UMCU: three are members of the internal DSMB of the UMCU and one member has clinical expertise as paediatric neurologist. Each member has no conflict of interest with the study. The task and responsibility of the DSMB are described in the DSMB charter. CVs of each DSMB member are added to the DSMB charter.

The DSMB may decide to terminate the trial prematurely using the stopping criteria as stated in chapter 6.7 of this protocol.

The advice(s) of the DSMB will only be sent to the sponsor of the study. Should the sponsor decide not to fully implement the advice of the DSMB, the sponsor will send the advice to the reviewing METC, including a note to substantiate why (part of) the advice of the DSMB will not be followed.

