8.3 Interim analysis (if applicable)

No interim analysis will be performed. Stopping rules are described in chapter 6.7. A DSMB will be established to advice on stopping, as is described in chapter 7.5 and in the DSMB Charter.

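### Section 6.7 halts the study after one death but not after one non-fatal MSC-related anaphylactic shock, the other event the protocol calls dose-limiting

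*Combined protocol and SAP*

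**What the plan says.** Section 1 (Primary Objective) defines safety first as no treatment-related serious adverse events, and second as the "absence of dose-limiting toxicity, defined as death within 24 hours after MSC transplantation or anaphylactic shock related to the MSC administration". Sections 6.1.1 and 8.1 repeat the definition, including "anaphylactic shock related to the MSC administration".

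Section 6.7 has four stopping rules. Three need 3 different patients: infarct growth above 20%, possibly related adverse effects, and unexplained clinical deterioration. The adverse-effects rule reads "If there appear to be any adverse effects that might be related to admission of MSCs in 3 different patients" and lists infection or meningitis, haemorrhagic transformation, gastrointestinal haemorrhage, thromboembolism and malignancy. The fourth rule needs one patient: "Mortality after treatment with MSCs in one patient will stop the study temporarily until an investigation has been performed". Anaphylactic shock appears in none of the four.

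Other provisions bear on the same event:

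- The opening of 6.7 permits early termination for adverse events, without a count.
- Section 7.1: "the sponsor will suspend the study if there is sufficient ground that continuation of the study will jeopardise subject health or safety". A suspension then lasts until the ethics committee gives a positive decision.
- Section 7.5: "The DSMB may decide to terminate the trial prematurely using the stopping criteria as stated in chapter 6.7 of this protocol". Section 8.3: "A DSMB will be established to advice on stopping".
- Section 2.4 says a DSMB has, "in addition to an internal safety review committee, been established to carry out further safety surveillance".
- Sections 7.2.2 and 7.2.3 require a preliminary report of a life-threatening serious event or SUSAR within 7 days. Section 11.2 adds 48-hour reporting of serious events and weekly review of adverse events with the Cell Therapy Facility.
- Sections 2.4 and 6.7 pause the study after infant 3 until the first three infants have had their 3-month MRI.

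**The concern.** The protocol names two events as dose-limiting, but only one has a mandatory response to a single case. After one related, survived anaphylactic shock, whether the next infant is dosed before the cause is understood depends on judgement and not on a written rule.

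This matters because the documents present the study as the first intranasal use of MSCs in humans, accept that risks may be unknown, and rely on the stopping rules in 6.7 to contain them (5.4, 9.4, 11.2). The point is narrow. It does not ask for a halt after every related serious event, only for the second event that the protocol itself puts beside early death.

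**Working it through.** **1. Does any provision require a halt after one non-fatal related shock?**

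| Provision | Effect of one related shock |
|---|---|
| 6.7, mortality rule | None; covers death only |
| 6.7, adverse-effects rule | At most 1 of 3, if the list is read as open-ended |
| 6.7, deterioration rule | At most 1 of 3 |
| 6.7, opening sentence | Termination permitted, not required |
| 7.1 | Suspension required only once grounds are judged sufficient |
| 7.5 and 8.3 | DSMB applies the 6.7 criteria and advises |
| 7.2.2, 7.2.3, 11.2 (reporting) | Informs others; does not pause dosing |
| 11.2 (acute reactions) | Monitoring and temperature control; no halt |
| Pause after infant 3 | Fixed in advance; does not act between infants 1 and 3 or after restart |

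None does.

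**2. How often would the rule matter?** The plan has no figure of its own to reproduce, and the documents give no anaphylaxis rate, so *p* is assumed. With *n* = 10 (3.4), P(at least one case) = 1 − (1 − p)^10:

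- p = 1%: 1 − 0.99^10 = 9.6%
- p = 2%: 1 − 0.98^10 = 18.3%
- p = 5%: 1 − 0.95^10 = 40.1%

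Counting shocks alone, P(3 or more of 10) is 0.01% at p = 1% and 1.2% at p = 5%. The three-patient rule would therefore almost never respond to shocks by themselves.

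**3. How many infants could be dosed after a first case?** Assume that no discretionary route is used, that each infant also has a probability *q* of another possibly related effect, and that dosing stops at 3 affected patients. The pause is credited: after a first case in infants 1 to 3, only infants up to number 3 count as further dosed.

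With q = 0 and small p, the first case is almost equally likely at each position. The further infants are then 2, 1, 0 (positions 1 to 3) and 6, 5, 4, 3, 2, 1, 0 (positions 4 to 10), a mean of 24/10 = 2.4. The exact recursion gives:

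| p | q = 0 | q = 5% | q = 10% | q = 20% |
|---|---|---|---|---|
| 1% | 2.41 | 2.33 | 2.16 | 1.77 |
| 2% | 2.42 | 2.33 | 2.16 | 1.76 |
| 5% | 2.43 | 2.32 | 2.14 | 1.75 |

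With q = 0, no further infant follows only if the first case is infant 3 or infant 10. The share with at least one further infant is therefore 1 − [p(1−p)² + p(1−p)⁹] / [1 − (1−p)^10]. At p = 1% this is 1 − (0.00980 + 0.00914)/0.0956 = 80%. Over all the p and q above, the range is 68% to 81%.

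**4. Would reporting come first?** Recruitment is 10 infants in 12 to 24 months (2.2, 3.4), a mean gap of about 5 to 10 weeks. With random arrivals at rate λ, P(next infant within t days) = 1 − exp(−λt):

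| λ per day | within 2 days | within 7 days |
|---|---|---|
| 10/730 | 2.7% | 9.1% |
| 10/365 | 5.3% | 17% |
| 10/639 (24 months less 91-day pause) | 3.1% | 10% |
| 10/274 (12 months less 91-day pause) | 7.0% | 23% |

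So the 7-day report would precede the next infant in about 77% to 91% of instances.

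**The case against.** The strongest reply is that the two thresholds need not match. Dose-limiting toxicity is an endpoint definition here; with one fixed dose and no escalation, it drives no dosing decision. The mortality rule is not derived from it either, because it covers death at any time and from any cause. That is fair: the difference is not a formal contradiction. Even so, the authors wrote an explicit halt for death although the same discretionary routes apply to death, and they give no reason for leaving out the only other event they call dose-limiting.

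Second, the existing safeguards are substantial. A suspension under 7.1 is mandatory once its condition is met, and only the ethics committee can lift it. A life-threatening related reaction that does not fit the Investigator's Brochure would be a SUSAR. The trial is single-centre and infants stay on the study NICU for at least 4 days (2.4), so the team would very probably know of the event. All of this stands and makes uninvestigated redosing unlikely, but it does not make a halt a requirement.

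Third, relatedness would still have to be judged under an amended rule. That is true, but it is a narrower question than whether there is sufficient ground to suspend the whole study.

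Fourth, the evidence of hazard is weak. Section 11.1e reports only mild allergic reactions in some studies, and no association with acute infusional toxicity in a meta-analysis covering 1012 patients. The assumed rates therefore illustrate the point and do not predict anything. Finally, the DSMB charter was not supplied and may already contain such a rule.

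**Conclusion.** The concern holds as a cheap improvement. On the text of 6.7, one death requires a halt and one non-fatal MSC-related anaphylactic shock does not. That reading is secure for the protocol; the charter remains unseen.

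The practical risk is modest. The figure of 1.75 to 2.43 further infants dosed per first case rests on assumed shock rates of 1% to 5%, on 0 to 20% of infants having another possibly related effect, and on every discretionary route going unused. The last assumption is pessimistic. The case for acting rests on the small cost of the change and on the weight the protocol places on its stopping rules.

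**What to change.** In the last stopping rule of 6.7, after the words on mortality following MSC treatment, insert: or "anaphylactic shock related to the MSC administration". The rest of the rule stays, so either event in one patient brings a temporary halt pending investigation. Check that the DSMB charter says the same.

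The cost is one clause and an occasional pause. At a true rate of 1%, about 10% of trials would halt for this reason. An eligible infant who presents during the halt could miss the 7-day treatment window. If the investigation took 4 weeks (assumed), the expected number presenting is 28 × 10/730 = 0.4 to 28 × 10/365 = 0.8, or up to 28 × 10/274 = 1.0 if the three-month pause is taken out of the recruitment period.
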